Study Objectives	 Primary Objectives To determine the maximum tolerated dose (MTD) of TGR-1202 when used in combination with ibrutinib in patients with relapsed or refractory CLL or MCL. To evaluate the safety and determine any dose limiting toxicities (DLTs) of TGR-1202 in combination with ibrutinib in patients with relapsed or refractory CLL or MCL. Secondary Objectives To preliminarily characterize the efficacy of TGR-1202 at its MTD in combination with ibrutinib by determining the overall response rate (ORR) defined as the sum of the complete response (CR) and partial response (PR) rate, as well as to determine the rate of nodal response with lymphocytosis (nPR), progression-free survival (PFS), and duration of response (DOR).

	Exploratory Objectives
	To assess whether apoptotic priming as determined by BH3 profiling and pharmacodynamic response as determined by phospho-flow are predictive of clinical response.
Efficacy Endpoints	 Efficacy Endpoints: Overall response rate, defined as sum of CR and PR rates. Responses will be determined according to response criteria as follows: MCL: International Working Group (Cheson et. al 2007; Revised Response Criteria for Malignant Lymphoma, [Appendix A]); CLL: International Workshop for Chronic Lymphocytic Leukemia (IW-CLL) Response Criteria (Hallek et al. 2008 [Appendix B]) as modified by Cheson et al., 2012.
Safety Endpoints	AEs will be evaluated during the treatment period and for 30 days following discontinuation from the study using CTCAE v4.0. The DLT observation period will be the first cycle (28 days).
	Up to 30 subjects per disease group (MCL and CLL/SLL), including a potential 12 qualified patients who will have completed the Phase Ib dose confirmation part of the study, may be enrolled. "Up to" is written because the Phase Ib can potentially stop early. Phase I Dose Confirmation:
	 3 + 3 design using Cycle 1 DLTs for both CLL/SLL and MCL patients, conducted independently in parallel, with a minimum of 3 patients in a cohort, as follows:
	 MCL: 3-6 patients at cohort 1 CLL/SLL: 3-6 patients at cohort 1
Study Design	• If no DLTs are reported among the initial in 3 patients in Cohort 1, the dose level will be considered safely cleared, and dose escalation may proceed to Cohort 2. If no DLTs are reported in 3 patients in Cohort 2, the dose will be considered safe for Cohort 3. If no DLT's are reported among the initial in 3 patients in Cohort 3, the Phase Ib part of the study will open.

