	• If 1 DLT is reported in either Cohort 1, 2 or 3, an additional 3 patients will be enrolled. If no additional DLTs are reported ($\leq 1/6$ pts), then dose escalation will continue to the next cohort or Phase Ib (if in Cohort 3 already).
	• If at least two patients experience a DLT in either Cohort 1 (MCL or CLL/SLL), the combination dose will be considered above the maximum tolerated dose and the dose Cohort -1 will enroll 3-6 patients. The same DLT rules will apply for Cohort -1 except if 2/6 patients experience a DLT in Cohort -1 the study will end for that respective group. If at least two

patients experience a DLT in Cohort 2 or 3, the next highest dose level which has cleared DLT evaluation will be considered the dose for the Phase Ib part of the study.

Phase Ib:

Once the dose has been confirmed separately for MCL and CLL/SLL patients, the Phase Ib will open and enroll up to 12 additional patients. The efficacy evaluation will include the 6 patients from the Ph I cohort dose for up to approximately 18 total patients evaluable for efficacy in each patient group (MCL & CLL/SLL).

[figure not shown]
Each Cycle = 28 days Cycle 1:

- TGR-1202 (oral): Starting on Day 1 administered daily in the morning with food, preferably within 30 minutes of a meal
- Ibrutinib (oral): Starting on Day 1 administered daily in the evening

Cycles 2 and >:

Daily treatment with both TGR-1202 and ibrutinib should continue. First efficacy assessment should be approximately 8 weeks (just prior to cycle 3) after Cycle 1/Day 1 (+/- 7 days) and approximately every 12 weeks thereafter (+/- 7 days) through cycle 12 following initiation of therapy (schema below).

Treatment Study Visits

After cycle 12, regular visits should occur every 3 cycles. After the Cycle 15 restaging, disease assessments should occur at least every 6 cycles (+/- 14 days) through cycle 36, at which point assessments can be done per investigator's discretion. After removal from study, patients should be followed for survival approximately every 3 months for up to 2 years

Baseline Lab Evaluation (Local Lab)

- CBC with differential
- Serum chemistry
- Serology to rule out active Hep B, C or HIV infection
- Serum pregnancy test
- FISH cytogenetic analysis
- *IGHV* mutation status (CLL patients only- Test performed by Integrated Oncology- See correlatives section 9.1.2.3)

Instrumenta l Tests

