11. MEASUREMENT OF EFFECT

Although response is not the primary endpoint of this trial, participants with measurable disease will be assessed by standard criteria. For the purposes of this study, the first efficacy assessment should be approximately 8 weeks after Cycle 1/Day 1 (+/- 7 days) and then just prior to cycles 6, 10 and 15. After cycle 15, efficacy assessments should occur at least every 6 cycles (168 +/- 14 days) until Cycle 36, where scans may be performed per investigator discretion.

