11.1 Antitumor Effect

Assessment of lymphoma response (CR, PR or SD) and disease progression will be evaluated as outlined in the schedule of events, according to the Revised Response Criteria for Malignant Lymphoma for MCL and SLL patients (26) and for CLL patients, the IWCLL Response Criteria (27) as modified by (28).

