A controversial issue is how best to categorize the response of patients who fulfill all the criteria for a CR (including the marrow examinations described above) but who have a persistent anemia or thrombocytopenia or neutropenia apparently unrelated to CLL but related to drug toxicity. We recommend that these patients be considered as a different category of remission: CR with incomplete marrow recovery (CRi). For the definition of this category, CRi, the marrow evaluation (described above) should be performed with scrutiny and not show any clonal infiltrate. In clinical trials, CRi patients should be monitored prospectively to determine whether their outcome differs from that of patients with detectable residual or with noncytopenic CR.

Partial Response: (PR)

To define a PR (partial remission): at least two of the criteria of Group A plus one of the criteria of Group B have to be met. The parameters below should be documented for no less than 2 months. Constitutional symptoms persisting for >1 month should be recorded.

Group A

- a. Decrease in the number of blood lymphocytes by 50% or more from the value before therapy.
- b. Reduction in lymphadenopathy (by PE and CT scans) as defined by the following:
 - A decrease in lymph node size by 50% or more either in the sum products of up to 6 lymph nodes, or in the largest diameter of the enlarged lymph node(s) detected prior to therapy.
 - No increase in any lymph node, and no new enlarged lymph node. In small lymph nodes (<2 cm), an increase of less than 25% is not considered to be significant.
- c. Reduction in the noted pretreatment enlargement of the spleen or liver by 50% or more, as detected by CT scan.

Group B

- d. Blood count should show one of the following:
 - Neutrophils >1.5 x $10^9/L$ ($1500/\mu L$) without need for exogenous growth factors.
 - Platelet count >100 x 10⁹/L (100 000/μL) or 50% improvement over baseline without need for exogenous growth factors.
 - Hemoglobin >110 g/L (11.0 g/dL), or 50% improvement over baseline without requiring red blood cell transfusions or exogenous erythropoietin.

Chronic Lymphocytic Leukemia Response Definition (Hallek et al. 2008) (continued)

Progressive	Progressive disease during or after therapy is characterized by at least one of the	
Disease:	following:	

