(PD)	 a. Lymphadenopathy: Progression of lymphadenopathy is often discovered by physical examination and should be recorded. In CLL, the use of CT scans usually does not add much information for the detection of progression or relapse. Therefore, the use of imaging methods to follow CLL progression is at the discretion of the treating physician. Disease progression occurs if one of the following events is observed: • Appearance of any new lesion, such as enlarged lymph nodes (>1.5 cm), splenomegaly, hepatomegaly, or other organ infiltrates. • An increase by 50% or more in greatest determined diameter of any previous site. b. An increase in the previously noted enlargement of the liver or spleen by 50% or more, or the de novo appearance of hepatomegaly or splenomegaly. c. An increase in the number of blood lymphocytes by 50% or more, with at least 5000 B-lymphocytes per μL. d. Transformation to a more aggressive histology (e.g., Richter syndrome). Whenever possible, this diagnosis should be established by lymph node biopsy. e. Occurrence of cytopenia (neutropenia, anemia, or thrombocytopenia) attributable to CLL • During therapy: Cytopenias may occur as a side effect of many therapies. During therapy, cytopenias cannot be used to define disease progression. • After treatment: The progression of any cytopenia (unrelated to autoimmune cytopenia), as documented by a decrease of Hb levels by >20 g/L (2 g/dL) or to <100 g/L (10 g/dL), or by a decrease of platelet counts by >50% or to <100 x 10°/L (100,000/μL), which occurs at least 3 months after treatment, defines disease progression, if the marrow biopsy demonstrates an infiltrate of clonal CLL cells. 	
Stable	Patients who have not achieved a CR, PR, or nPR and who have not exhibited	
Disease:	progressive disease, will be considered to have stable disease (which is equivalent	
(SD)	to a non-response).	
Nodular	As per Cheson et al., 2012, patients who achieve a radiographic PR but continue to	
Partial	have a lymphocytosis with $>5,000$ B-lymphocytes per μL are considered to have a	
Response	nodular partial response, also known as PR with lymphocytosis, due to the fact that	
(nPR)	they appear to derive a similar clinical benefit from BCR inhibitors as patients who achieve a traditional PR.	

Phase I/Ib Study of TGR-1202 plus Ibrutinib in Patients with Select B-Cell Malignancies Version Date: 10.23.2019

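### Appendix B's CLL progression item c has no on-treatment exemption for the lymphocytosis that section 11.2.2 expects; the nPR row and CR timing also need aligning

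*Combined protocol and SAP*

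**What the plan says.** **Which rule applies.** Section 11.2 sends CLL to Appendix B, and SLL and MCL to Appendix A. Section 11.2.3 again refers to the appendices for best response. The synopsis names "CLL: International Workshop for Chronic Lymphocytic Leukemia (IW-CLL) Response Criteria" of 2008, points to Appendix B, and adds that they apply as modified in 2012. Section 11.1 has "for CLL patients, the IWCLL Response Criteria (27) as modified by (28".

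**Progression.** The Appendix B lead-in is "Progressive disease during or after therapy is characterized by at least one of the" items that follow. Item c is "An increase in the number of blood lymphocytes by 50% or more, with at least 5000 B-lymphocytes per" µL. Item e, in the same list, says "During therapy, cytopenias cannot be used to define disease progression". Item c has no such sentence.

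**Lymphocytosis on study drug.** Section 11.2.2 expects it in many patients, mainly in the CLL arm, as a class effect of BCR inhibitors. It defines nPR as a radiographic PR with more than 5,000 B-lymphocytes/µL and an absolute lymphocyte count (ALC) that has not fallen by at least half. The Appendix B row for nPR leaves out the ALC condition and calls the category *nodular*, a term the appendix also uses for lymphoid nodules in marrow.

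**CR.** Appendix B times CR at 2 months or more after therapy ends, and its marrow at 2 months or more after the last treatment. Section 5.2 continues daily dosing until progression or removal. Section 5.4.12 and note 2 of the study calendar provide marrow to confirm CR; note 2 ties it to a radiographic CR.

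**Timing of assessments.** Under section 11.1, "disease progression will be evaluated as outlined in the schedule of events". Section 11 adds that "the first efficacy assessment should be approximately 8 weeks after Cycle 1/Day 1 (+/- 7 days").

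**The concern.** A rise in circulating lymphocytes while nodes shrink is something the protocol itself treats as a benign drug effect. Item c, taken at its word, scores the same rise as progression. Because item e contains an explicit on-therapy exemption, a reader cannot assume that a similar one is implied for item c.

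The label matters for several endpoints. Progression is a PFS event (section 11.2.5), it ends duration of response (11.2.4), and best response counts only what is recorded before it (11.2.3). A patient scored as progressing at the first assessment could therefore not be credited with a later PR or CR. Progression is also a listed reason to stop treatment in section 5.8, although that section lets a patient with clinical benefit continue.

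Two assessors could each follow the protocol and classify the same patient differently. The shortened nPR row and the post-therapy CR timing raise smaller questions of the same kind.

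**Working it through.** The plan gives no figure on this point, so there is none to reproduce. The check applies the written rules to example patients. The counts are illustrative, and nearly all lymphocytes are assumed to be B-cells. The progression reference is the smallest value since treatment started (11.2.3), here the starting count.

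**Patient 1: nodes smaller but short of a radiographic PR; ALC 20,000 to 35,000/µL.**
- Change: 35,000/20,000 − 1 = +75%. Item c needs +50%, that is 20,000 × 1.5 = 30,000/µL, with at least 5,000 B-cells/µL. Both are met.
- Section 11.2.2 does not apply, because there is no radiographic PR.
- The stable-disease row requires that progression has not occurred, so it does not help.
- Written result: progression. Nothing in the protocol's own text says otherwise.

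**Patient 2: radiographic PR; ALC 20,000 to 35,000/µL.**
- Section 11.2.2: ALC has not halved and exceeds 5,000/µL, so nPR.
- Item c: +75%, so progression.
- Written result: two labels. The specific section favours nPR, but no sentence switches item c off.

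**Patient 3: radiographic PR; ALC 100,000 to 40,000/µL; one Group B count met; findings documented for the required 2 months.**
- Change: 40,000/100,000 − 1 = −60%. Group A items a and b are met, so PR.
- The Appendix B nPR row also fits, because 40,000 exceeds 5,000 and the row has no ALC condition. Section 11.2.2 excludes nPR.
- The overlap needs a fall of at least 50% that still leaves more than 5,000/µL, so a baseline above 5,000/0.5 = 10,000/µL.
- ORR is CR plus PR, so the label decides whether the patient counts.

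**Patient 4: all CR findings while on drug.**
- Appendix B timing cannot be met during continuous dosing.
- Section 5.4.12 and calendar note 2 provide for confirming this CR. The two texts conflict.

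**Size per patient.** The synopsis plans "up to approximately 18 total patients evaluable for efficacy in each patient group".
- One reclassified patient: 1/18 = 5.6 percentage points of a response rate.
- One lymphocytosis-only progression at about week 8 lowers the Kaplan-Meier PFS curve by the same 1/18 = 5.6 points, if all 18 are still at risk.
- SLL patients follow Appendix A, and the CLL/SLL split is not given. If 15 or 12 of the 18 had CLL (assumption), the shift in a CLL-only rate is 1/15 = 6.7 or 1/12 = 8.3 points.

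**Citations in section 11.1.** It cites (27) as modified by (28). The reference list ends at 27, which is the 2012 paper; the 2008 guideline is 25.

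**The case against.** The strongest reply is that Appendix B is not the whole rule. The synopsis and section 11.1 adopt the criteria as modified in 2012, and the synopsis, section 11.2.2 and the nPR row identify that source well enough despite the wrong numbers in 11.1. A reader might infer that the trial has no exemption for lymphocytosis at all. The documents do not support that: the modification is adopted by reference, and its text on progression is not reproduced. What can be said is that no exemption is written where assessors are sent.

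Three further readings go too far.
- *ORR is left undefined for patients like patient 3.* Section 11.2.2 supplies the missing ALC condition, section 11.2.3 takes the best response, and the nPR row sets itself apart from a conventional PR. The intended answer is PR.
- *No patient on drug can be a CR.* The synopsis, sections 5.4.12 and 9.1.2.1, note 8 to the sample table in 9.1.2.5 and calendar note 2 together show that on-treatment CR is intended. The appendix timing is retained guideline text.
- *A predictable share of patients will be misclassified.* The documents give no rate of lymphocytosis-only progression for this combination.

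For patient 2, the reply that the specific section should prevail over general appendix text is reasonable. It does not reach patient 1, for whom section 11.2.2 says nothing.

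**Conclusion.** The concern holds as a gap in item c, with two alignment points beside it. Item c as written makes isolated, drug-related lymphocytosis on treatment a progression. The case is clearest for nodal shrinkage short of a radiographic PR. With a radiographic PR, the protocol points to nPR without removing the contrary instruction. The nPR row and the CR timing disagree with other sections whose intent is clear, so those are edits to bring the texts into line.

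The scope is narrow: CLL patients only, and PFS, duration of response, best response/ORR, nPR and CR, all secondary and largely descriptive under section 13.4. MTD, DLT rules and sample size are untouched. Each affected patient is worth about 5.6 points at the planned maximum of about 18; how many there would be is unknown. Severity: minor to moderate clarification of secondary endpoints. The conclusion rests on the protocol's own text and assumes nothing about what the 2012 paper says on progression.

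**What to change.** Amend Appendix B and section 11.1.

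- **(a) Item c.** While the patient is on study drug, lymphocytosis that began after starting drug is not progression unless item a, b or d is also met. Cytopenias during therapy stay under item e and do not remove the exemption; otherwise a drug-related neutropenia with lymphocytosis would become progression, contrary to item e. Keep item c for patients off drug, and for a rise of 50% or more from nadir after an earlier lymphocyte response or normalisation. Section 11.1.2 allows CLL patients whose only measurable disease is in blood or marrow; the sponsor should set an explicit progression rule for them.
- **(b) nPR row.** Replace it with the section 11.2.2 definition, label it *nodal PR (PR with lymphocytosis)*, and state that a patient who meets the full PR criteria is a PR.
- **(c) CR.** State that CR is assessed on treatment, with marrow at radiographic CR as in section 5.4.12 and calendar note 2.
- **(d) Citations.** In section 11.1, cite (25) as modified by (27).

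The cost is a short wording amendment. It uses ALC, CT and marrow data that the protocol already collects, with no new procedures or patients. The downside is some judgement in attributing lymphocytosis to the drug.

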APPENDIX C CONTRACEPTIVE GUIDELINES AND PREGNANCY

Women Not of Childbearing Potential are Defined as Follows:

Women are considered post-menopausal and not of child bearing potential if they have had 12 months of natural (spontaneous) amenorrhea with an appropriate clinical profile (e.g. age appropriate, history of vasomotor symptoms) or six months of spontaneous amenorrhea with serum FSH levels > 40 mIU/mL [for US only: and estradiol < 20 pg/mL] or have had surgical bilateral oophorectomy (with or without hysterectomy) at least six weeks ago. In the case of oophorectomy alone, only when the reproductive status of the woman has been confirmed by follow up hormone level assessment is she considered not of child bearing potential. A tubal ligation is also sufficient documentation that a patient is not of child bearing potential for this trial.

Contraceptive Guidelines for Women of Child-Bearing Potential:

Women of child-bearing potential, defined as all women physiologically capable of becoming pregnant, must use highly effective contraception during the study and for additional 4 weeks after study drug discontinuation. The highly effective contraception is defined as either:

- 1. True abstinence: When this is in line with the preferred and usual lifestyle of the subject. Periodic abstinence (e.g., calendar, ovulation, symptothermal, post-ovulation methods) and withdrawal are not acceptable methods of contraception.
- 2. Sterilization: have had surgical bilateral oophorectomy (with or without hysterectomy) or tubal ligation at least six weeks ago. In case of oophorectomy alone, only when the reproductive status of the woman has been confirmed by follow up hormone level assessment.
- 3. Male partner sterilization (with the appropriate post-vasectomy documentation of the absence of sperm in the ejaculate). For female subjects on the study, the vasectomised male partner should be the sole partner for that patient.
- 4. Use of a combination of any two of the following (a+b):
 - a. Placement of an intrauterine device (IUD) or intrauterine system (IUS).
 - b. Barrier methods of contraception: Condom or Occlusive cap (diaphragm or cervical/vault caps) with spermicidal foam/gel/film/cream/vaginal suppository.

The following are unacceptable forms of contraception for women of childbearing potential:

- Oral contraception, injected or implanted hormonal methods are not allowed as ibrutinib potentially decreases the effectiveness of hormonal contraceptives.
- IUD progesterone T
- Female condom
- Natural family planning (rhythm method) or breastfeeding
- Fertility awareness
- Withdrawal

Phase I/Ib Study of TGR-1202 plus Ibrutinib in Patients with Select B-Cell Malignancies Version Date: 10.23.2019

• Cervical shield

Women of child-bearing potential must have a negative serum or urine pregnancy test \leq 72 hours prior to initiating treatment.

Fertile Males:

Fertile males, defined as all males physiologically capable of conceiving offspring must use condom during treatment, for additional 4 weeks after study drug discontinuation, and should not father a child in this period.

Pregnancies

To ensure patient safety, each pregnancy in a patient on study treatment must be reported to TG Therapeutics Inc. within 24 hours of learning of its occurrence. The pregnancy should be followed up for 3 months after the termination of the pregnancy to determine outcome, including spontaneous or voluntary termination, details of the birth, and the presence or absence of any birth defects, congenital abnormalities, or maternal and/or newborn complications. Pregnancy should be recorded on a Clinical Study Pregnancy Form and reported by the investigator to TG Therapeutics Inc. Pregnancy follow-up should be recorded on the same form and should include an assessment of the possible relationship to the study drug and reported by the investigator to TG Therapeutics Inc. Any SAE experienced during pregnancy must be reported on the SAE Report Form.

Pregnancy outcomes must be collected for the female partners of any males who took study treatment in this study. Consent to report information regarding these pregnancy outcomes should be obtained from the mother.

